4.2. Exclusion Criteria

A patient must not meet any of the following exclusion criteria to be eligible for participation in this study; waivers will not be granted for any of the eligibility criteria.

1. Have received prior therapy with anti-PD-1, anti-PD-L1/L2 agent.
2. Have received prior FGFR inhibitor treatment including futibatinib
3. History and/or current evidence of any of the following disorders:
 - a. Non-tumor related alteration of the calcium-phosphorus homeostasis that is considered clinically significant in the opinion of the Investigator

- b. Ectopic mineralization/calcification, including but not limited to soft tissue, kidneys, intestine, or myocardia and lung, considered clinically significant in the opinion of the Investigator
- c. Retinal or corneal disorder confirmed by retinal/corneal examination and considered clinically significant in the opinion of the Investigator.

4. Corrected QT interval using Fridericia's formula (QTcF) >470 msec. Patients with an atrioventricular pacemaker or other condition (for example, right bundle branch block) that renders the QT measurement invalid are an exception and the criterion does not apply.

5. Has received major surgery within the previous 4 weeks.

6. Has received any non-investigational anticancer therapy within the previous 3 weeks (mitomycin within the previous 5 weeks).

7. Is currently participating in a study of an investigational agent/device, or has participated in a study of an investigational agent or used an investigational device within 4 weeks prior to the first dose of study treatment.

8. Has received a live vaccine within 30 days prior to the first dose of study drug. Examples of live vaccines include, but are not limited to, the following: measles, mumps, rubella, varicella/zoster (chicken pox), yellow fever, rabies, *Bacillus Calmette–Guérin* (BCG), and typhoid vaccine. Seasonal influenza vaccines for injection are generally killed virus vaccines and are allowed; however, intranasal influenza vaccines (e.g., FluMist®) are live attenuated vaccines and are not allowed.

9. A serious illness or medical condition(s) including, but not limited to, the following:

- a. Has an active infection requiring systemic therapy.
- b. Myocardial infarction, severe/unstable angina, or symptomatic congestive heart failure within the previous 6 months
- c. History or current evidence of uncontrolled ventricular arrhythmia
- d. Chronic diarrhea diseases considered to be clinically significant in the opinion of the Investigator
- e. Congenital long QT syndrome, or any known history of torsade de pointes, or family history of unexplained sudden death
- f. Have an active autoimmune disease that has required systemic treatment in the past 2 years (that is, with use of disease modifying agents, corticosteroids, or immunosuppressive drugs). Replacement therapy (for example, thyroxine, insulin, or physiologic corticosteroid replacement therapy for adrenal or pituitary insufficiency) is not considered a form of systemic treatment and is allowed.
- g. Have a history of (noninfectious) pneumonitis that required steroids or has current pneumonitis.
- h. Have had an allogenic tissue/ organ transplant.

10. Has known human immunodeficiency virus (HIV) and/or history of Hepatitis B or C infections, or known to be positive for Hepatitis B antigen (HBsAg)/ Hepatitis B virus (HBV) DNA or Hepatitis C Antibody or RNA. Active Hepatitis C is defined by a known positive Hep C Ab result and known quantitative HCV RNA results greater than the lower limits of detection of the assay.
11. Has a history or current evidence of any condition, therapy, or laboratory abnormality that might confound the results of the study, interfere with the participant's participation for the full duration of the study, or is not in the best interest of the participant to participate, in the opinion of the treating Investigator.
12. Have known active central nervous system metastases and/or carcinomatous meningitis. Patients with previously treated brain metastases may participate provided they are radiologically stable, that is, without evidence of progression for at least 4 weeks by repeat imaging (note that the repeat imaging should be performed during study screening), clinically stable, and without steroid treatment requirement for at least 1 month prior to the first dose of study treatment.
13. The patient is pregnant or breastfeeding.
14. Has a diagnosis of immunodeficiency or is receiving chronic systemic steroid therapy (in dosing exceeding 10 mg daily of prednisone equivalent) or any other form of immunosuppressive therapy within 7 days prior the first dose of study drug.
15. Has a known additional malignancy that is progressing or has required active treatment within the past 2 years. Participants with basal cell carcinoma of the skin, squamous cell carcinoma of the skin, or carcinoma in situ (e.g., breast carcinoma, cervical cancer in situ) that have undergone potentially curative therapy are not excluded.
16. Has severe hypersensitivity (\geq Grade 3) to pembrolizumab and/or any of its excipients.
17. Has a known psychiatric or substance abuse disorder that would interfere with the participant's ability to cooperate with the requirements of the study.

4.3. Screen Failure

Screen failures are defined as patients who consent to participate in the clinical study but are not subsequently enrolled in the study. A minimal set of screen failure information is required to ensure transparent reporting of screen failure patients to respond to queries from regulatory authorities. Minimal information includes demography, screen failure details, eligibility criteria, and any SAE after completion of the ICF.

Patients who do not meet the criteria for participation in this study (screen failure) may be rescreened a maximum of 3 times. Rescreened patients should be assigned the same subject identification code as for the initial screening.

4.4. Discontinuation of Treatment

Pembrolizumab may be administered for a maximum of 35 doses or a maximum duration of 2 years, whichever is earlier. There is no maximum duration of futibatinib therapy. A patient will be discontinued from any or all study therapy for any of the following reasons:

1. Disease progression
2. Unacceptable AEs, or change in underlying condition such that the patient can no longer tolerate therapy, as evidenced by a dose delay > 21 days from the scheduled start date of the next cycle or need for more than 2 dose reductions outlined in this protocol. If such toxicity is associated with only 1 of the treatment components (futibatinib or pembrolizumab), the patient may discontinue that component and continue receiving the other if medically appropriate in the opinion of the Investigator.
3. Physician’s decision, including need for other anticancer therapy not specified in the protocol or surgery or radiotherapy to the only site(s) of disease being followed in the study
4. Pregnancy
5. Termination of the study by the Sponsor, or
6. At the patient’s request at any time irrespective of the reason.

Patients who withdraw consent for further treatment may choose to remain on study; in such a case, all study evaluations should continue as outlined in this protocol. If the patient withdraws consent to all follow-up assessments, the patient should be considered to have discontinued the study as described in [Section 4.5](#).

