5. STUDY TREATMENT

5.1. Study Drug Administration

Please note: at any timepoint where futibatinib and pembrolizumab are administered on the same day, pembrolizumab should be administered prior to futibatinib if possible. A study cycle is defined as 21 days.

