5.1.2. Pembrolizumab

Pembrolizumab is administered as an I.V. infusion of 200 mg on Day 1 of each cycle (that is, every 3 weeks). Treatment continues for a maximum of 35 doses or a maximum duration of 2 years (whichever is earlier), or until the patient meets any of the administration discontinuation criteria (see [Section 4.4](#)).

Pembrolizumab should be administered according to the instructions on the approved product label.

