5.2. Definition of Dose-Limiting Toxicity

For this study, unacceptable toxicity will include any event meeting the criteria for dose-limiting toxicity (DLT), as outlined below. An adverse event not meeting the criteria for a DLT may also be considered an unacceptable toxicity, if it is not tolerable in the long-term and necessitates discontinuation of one or more elements of the combination therapy.

DLT Definition

All toxicities will be graded using the National Cancer Institute – Common Terminology Criteria for Adverse Events (NCI-CTCAE) Version 5.0, based on Investigator assessment. The occurrence of any of the following toxicities during Cycle 1 will be considered a DLT, if assessed by the Investigator to be related to study treatment administration.

- Grade 4 nonhematologic toxicity (not laboratory)
- Grade 4 neutropenia lasting >5 days
- Grade 4 thrombocytopenia of any duration

- Grade 3 thrombocytopenia associated with clinically significant bleeding
- Any nonhematologic AE \geq Grade 3 in severity, with the following exceptions:
 - Grade 3 fatigue lasting \leq 3 days;
 - Grade 3 diarrhea, nausea, or vomiting without use of anti-emetics or anti-diarrheals per standard of care;
 - Grade 3 rash without use of corticosteroids or anti-inflammatory agents per standard of care.
- Any Grade 3 or Grade 4 nonhematologic laboratory value if:
 - Clinically significant medical intervention is required to treat the patient, or
 - The abnormality leads to hospitalization, or
 - The abnormality does not recover to Grade \leq 1 within 48 hours despite best supportive care, or
 - The abnormality results in a drug induced liver injury
 - Exceptions: clinically nonsignificant, treatable, or reversible laboratory abnormalities including liver function tests, uric acid, hyperphosphatemia, etc.
- Febrile neutropenia Grade 3 or Grade 4:
 - Grade 3 is defined as ANC $<1000/\text{mm}^3$ with a single temperature of $>38.3^\circ\text{C}$ (101°F) or a sustained temperature of $\geq38^\circ\text{C}$ (100.4°F) for more than 1 hour
 - Grade 4 is defined as ANC $<1000/\text{mm}^3$ with a single temperature of $>38.3^\circ\text{C}$ (101°F) or a sustained temperature of $\geq38^\circ\text{C}$ (100.4°F) for more than 1 hour, with life-threatening consequences and urgent intervention indicated.
- Grade 3 or higher visual impairment
- Prolonged delay (>2 weeks) in initiating Cycle 2 due to treatment-related toxicity

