5.3.3. Dose Modifications for Pembrolizumab

5.3.3.1. Dose Modification and Toxicity Management for Immune-Related AEs Associated with Pembrolizumab

AEs associated with pembrolizumab exposure may represent an immune-related (ir) response. These irAEs may occur shortly after the first dose or several months after the last dose of pembrolizumab treatment and may affect more than one body system simultaneously. Therefore, early recognition and initiation of treatment is critical to reduce complications. Based on existing clinical study data, most irAEs were reversible and could be managed with interruptions of pembrolizumab, administration of corticosteroids and/or other supportive care. For suspected irAEs, ensure adequate evaluation to confirm etiology or exclude other causes. Additional procedures or tests such as bronchoscopy, endoscopy, skin biopsy may be included as part of the evaluation.

General instructions for the management of irAEs are as follows; please see [Table 8](#) for detailed guidelines.

1. Severe and life-threatening irAEs should be treated with I.V. corticosteroids followed by oral steroids. Other immunosuppressive treatment should begin if the irAEs are not controlled by corticosteroids.
2. Pembrolizumab must be permanently discontinued if the irAE does not resolve or the corticosteroid dose is not ≤ 10 mg/day within 12 weeks of the last pembrolizumab treatment.
3. The corticosteroid taper should begin when the irAE is \leq Grade 1 and continue at least 4 weeks.
4. If pembrolizumab has been withheld, pembrolizumab may resume after the irAE decreased to \leq Grade 1 after corticosteroid taper.

Table 8: Guidelines for Management of Immune-Related Adverse Events Associated with Pembrolizumab

irAEs	Toxicity grade or conditions (CTCAE V5.0)	Action with pembrolizumab	Corticosteroid and/or other therapies	Monitoring and follow-up
Pneumonitis	Grade 2	Withhold	
 Administer corticosteroids (initial dose of 1-2 mg/kg prednisone or equivalent) followed by taper Add prophylactic antibiotics for opportunistic infections 	
 Monitor patients for signs and symptoms of pneumonitis Evaluate patients with suspected pneumonitis with radiographic imaging and initiate corticosteroid treatment
	Recurrent Grade 2, Grade 3 or 4	Permanently discontinue		

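### A patient ready to restart pembrolizumab 43 to 84 days after the last infusion, following an immune-related adverse event, may resume under Protocol 5.3.3.1 but is discontinued under Protocol 4.4, and nothing says which rule governs

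*Protocol*

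**What the plan says.** **Protocol 4.4, Discontinuation of Treatment.** The list of reasons opens in mandatory terms: "A patient will be discontinued from any or all study therapy for any of the following reasons". Item 2 covers unacceptable adverse events, or a change in the patient's condition, such that therapy can no longer be tolerated, "as evidenced by a dose delay > 21 days from the scheduled start date of the next cycle" or by the need for more than two dose reductions. The rule can apply to one drug alone: "If such toxicity is associated with only 1 of the treatment components (futibatinib or pembrolizumab), the patient may discontinue that component" and stay on the other. Protocol 5.1.2 lists the 4.4 criteria among the reasons to stop pembrolizumab.

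**Protocol 5.3.3.1, irAEs associated with pembrolizumab.** Permanent discontinuation is required if the irAE has not resolved, or the steroid dose has not come down to 10 mg/day or less, "within 12 weeks of the last pembrolizumab treatment". On the taper: "The corticosteroid taper should begin when the irAE is" Grade ≤1, and it lasts at least 4 weeks. Pembrolizumab that was withheld may restart once the event is Grade ≤1, after the taper. Table 8 directs a hold with steroids and taper for, among others, Grade 2 pneumonitis, Grade 2 or 3 diarrhea/colitis, Grade 2 liver events and Grade 2 nephritis.

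**Protocol 5.3.3.3** has a separate 3-week limit, with an exception by discussion with the Sponsor. It covers only interruptions that are not due to treatment-related adverse events.

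**Protocol 5.2** allows an event that is not a dose-limiting toxicity (DLT) to be considered unacceptable toxicity "if it is not tolerable in the long-term and necessitates discontinuation of one or more elements of the combination therapy".

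**The concern.** Section 4.4 and Section 5.3.3.1 both decide whether pembrolizumab stops after a toxicity hold. Their time limits differ and run from different dates. Neither section refers to the other, and neither says which prevails for an irAE. Two sites following the protocol correctly could therefore treat the same recovered patient in opposite ways.

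Three things depend on the answer:

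- **Exposure.** One of the two study drugs is either restarted or lost for good. This feeds the exposure and relative dose intensity summaries in SAP 5.5.1.1.
- **Safety tables.** SAP 5.5.1.2 tabulates interruptions and discontinuations separately, and SAP 5.5.2.3 and 5.5.2.4 do the same for the adverse events that lead to them. The same patient can be counted as interrupted only, or as discontinued too, according to the section the site read.
- **Stopping rule.** Discontinuing one element of the combination is part of the 5.2 definition of unacceptable toxicity, which is what the 33% intolerability criterion counts.

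**Working it through.** The plan gives no figure of its own to reproduce. The check is to put both rules on one clock, days since the last pembrolizumab infusion (day 0).

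**Inputs from the Protocol**
- Cycle length: "A study cycle is defined as 21 days" (5.1). Pembrolizumab is given on Day 1 of each cycle (5.1.2).
- 4.4 limit: 21 days past the scheduled start of the next cycle.
- 5.3.3.1 limit: 12 weeks from the last infusion.
- Minimum taper: 4 weeks = 28 days, starting at Grade ≤1.

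**Step 1. Common clock**
- 4.4: 21 + 21 = day 42.
- 5.3.3.1: 12 × 7 = day 84.
- Measured past the scheduled dose: 42 − 21 = 21 days (3 weeks) against 84 − 21 = 63 days (9 weeks).
- Overlap: days 43 to 84, which is 84 − 42 = 42 days.

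| Ready to resume | Under 4.4 | Under 5.3.3.1 |
|---|---|---|
| By day 42 | May continue | May resume |
| Days 43–84 | Discontinued | May resume |

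**Step 2. Effect of the taper, if it must be completed**
- To resume by day 42: Grade ≤1 by 42 − 28 = day 14.
- To resume by day 84: Grade ≤1 by 84 − 28 = day 56.
- Grade ≤1 reached on days 15 to 56 therefore falls in the overlap. The 28-day taper is longer than 21 days but fits within 42, so it does not by itself breach 4.4.

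**Step 3. How many holds would be affected**

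The documents give no irAE timing, so this is a sensitivity calculation on assumptions. Let onset be uniform over the 21 days after the infusion, let time to Grade ≤1 be a fixed t days, and let the 28-day taper be completed. A hold is in conflict when 14 < onset + t ≤ 56. The share is (7 + t)/21 for t up to 14, 100% for t from 14 to 35, and (56 − t)/21 for t from 35 to 56.

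| t (days) | Share in conflict |
|---|---|
| 0 | 7/21 = 33% |
| 3.5 | 10.5/21 = 50% |
| 7 | 14/21 = 67% |
| 14 to 35 | 100% |
| 42 | 14/21 = 67% |
| 45.5 | 10.5/21 = 50% |
| 56 | 0% |

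With exponential times to Grade ≤1 (medians 3 to 56 days) the share lies between 37% and 70%. If resumption is allowed 7 or 14 days after Grade ≤1, before the taper ends, it lies between 1% and 42% (medians 3 to 28 days). The overlap is fixed by the text, but the share of holds falling in it is not.

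**Step 4. Reach into the stopping rule**
- Protocol 5.2 already makes a treatment-related delay of more than 2 weeks in initiating Cycle 2 a DLT. That limit is 21 + 14 = day 35, which comes before day 42.
- A related Cycle 1 irAE that delays Cycle 2 is therefore counted before the 4.4 limit is reached.
- Two cases stay open. One is a hold that begins after Cycle 1. The other is a hold where Cycle 2 is taken to have started on futibatinib alone, so that the DLT item is not met, while 4.4 is still applied to pembrolizumab separately.

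**The case against.** Five arguments can be made that there is no real contradiction.

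1. **Two stopping rules can coexist.** Item 2 of 5.3.3.1 is itself a mandatory stop and does not grant a 12-week hold, and resumption is permissive. This stands as a point of wording: a reader might infer that the protocol permits 12-week holds, and it does not say so. Day 84 is also not worded as a resumption deadline. But if both rules apply, 4.4 has already removed the patient after day 42, and the 12-week clause has almost nobody left to act on.
2. **4.4 requires intolerance, of which the delay is only evidence.** A recovered irAE arguably does not qualify. However, the delay is the evidence that 4.4 names, and no exception is made for recovery.
3. **The specific rule governs.** Protocol 5.3.1 ties futibatinib's 21-day rule to 4.4, while 5.3.3.1 has no such reference. This is plausible, but 5.1.2 sends pembrolizumab to 4.4 and no passage gives 5.3.3.1 precedence.
4. **The cycle starts on time if futibatinib continues.** Then 4.4 is not triggered. The sentence on stopping one component, and 5.1.2, weigh against this without settling it.
5. **The taper need not be completed.** Item 4 of 5.3.3.1 does not say completed, item 2 uses 10 mg/day rather than zero, and Table 8 note d allows resumption without mentioning a taper. This stands. The day-14 cutoff is conditional on a full taper, although the 42- and 84-day limits are not.

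The competing readings are reasons to settle the text. They do not show that it is already settled.

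**Conclusion.** The contradiction is in the text. For a patient ready to resume on days 43 to 84 after the last infusion, 5.3.3.1 allows resumption and 4.4 requires discontinuation, and no passage says which applies. This rests on the 21-day cycle and on 4.4 applying to pembrolizumab separately. The day-14 cutoff for reaching Grade ≤1 rests further on a completed 4-week taper.

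The consequence that can be shown is for pembrolizumab exposure and for the SAP's interruption and discontinuation tables. DOR and PFS are affected only indirectly, because Protocol 3.2.3 and Section 8 continue scans after treatment stops without progression.

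Two stronger conclusions are tempting and are not supported:

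- A reader might infer that most steroid-treated holds fall in the conflict. The documents give no irAE timing, and the share runs from 0% to 100% under the assumptions tried.
- A reader might infer that one reclassified patient at the first safety look moves the count from 1/6 (17%) to 2/6 (33%) and so meets the intolerability criterion. That look follows Cycle 1, and the delay item in the DLT list already captures a related irAE that holds up Cycle 2 by more than 2 weeks.

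What remains for the stopping rule is holds after Cycle 1, or Cycle 2 treated as started on futibatinib alone. If that last reading is applied equally to 4.4, its limit is not triggered either. Outside the DLT list, 5.2 is discretionary and also asks that the event be intolerable in the long term, so a later-cycle hold might count but need not.

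**What to change.** Reconcile Protocol 4.4 item 2, 5.1.2 and 5.3.3.1 with Table 8:

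- State in 4.4 which time limit governs pembrolizumab held for an irAE and which governs futibatinib.
- State the date from which each limit is counted. At present 4.4 counts from the scheduled next cycle, 5.3.3.1 from the last pembrolizumab infusion, and 5.3.1 from the last futibatinib dose. Table 5 adds a 4-week period for reversal of eye toxicity, which should be checked against the same rule.
- Say whether the taper must be completed before resumption, and whether a cycle counts as started when only one drug is given.
- Add cross-references so that each section names the one that governs.
- State in 5.2 whether a later-cycle pembrolizumab hold that is resumed under 5.3.3.1 counts as unacceptable toxicity.

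The choice of limit is the sponsor's. The cost is a wording change in the next protocol amendment, with no added patients or procedures.

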4.5. Withdrawal from the Study

A patient may be withdrawn from all study interventions and assessments (that is, discontinued from the study without follow-up) for any of the following reasons:

1. Death
2. Lost to follow-up
 - A participant will be considered lost to follow-up if he or she repeatedly fails to return for scheduled visits and is unable to be contacted by the study site.
 - The following actions must be taken if a patient fails to return to the clinic for a required study visit:
 - The site must attempt to contact the patient and reschedule the missed visit as soon as possible and counsel the patient on the importance of maintaining the assigned visit schedule and ascertain whether or not the patient wishes to and/or should continue in the study.
 - Before a patient is deemed lost to follow up, the Investigator or designee must make every effort to regain contact with the patient (where possible, 3 telephone calls and, if necessary, a certified letter to the patient’s last known mailing address or local equivalent methods). These contact attempts should be documented in the patient’s medical record.
 - Should the patient continue to be unreachable, he/she will be considered to have withdrawn from the study.

3. Patient withdrawal of consent to further follow-up assessments, irrespective of the reason.

